Subjects will complete a variety of diagnostic, cognitive and psychological assessments, a comprehensive physical examination and blood work. If completing the laboratory component as inpatients, subjects will also be involved in development of imagery scripts from personal stress, drug-related cue and neutral situations during the first 3 weeks of their stay. After subjects have been substance- free for 21+ days, they will participate in an imagery/relaxation training and

habituation session. Between weeks 3 – 4, subjects will participate in a 3-day experiment in which during a 2-hour laboratory session on three consecutive days, subjects will be exposed by guided imagery to a personal stressful situation, a drug cue related situation and a neutral relaxing situation, one exposure per day. Order of imagery type will be randomly assigned across subjects.

Research Plan:

Subjects will have the option of participating in either the inpatient–outpatient plan, or the outpatient plan. The inpatient–outpatient plan involves 3 - 4 weeks of inpatient treatment followed by 8 - 9 weeks of outpatient treatment. Subjects completing the inpatient-outpatient plan may or may not complete the laboratory sessions. The outpatient plan involves outpatient treatment with 12-Step Counseling for 12 weeks. Subjects enrolled in the outpatient plan also have the option to complete 4 days of inpatient laboratory sessions. The provision of an outpatient alternative is added to provide an opportunity for participation to those subjects who are not able to participate in longer inpatient treatment due to childcare, employment, or other related obligations. The three alternatives are described below:

Inpatient-Outpatient Plan with laboratory sessions:

Once a subject is deemed eligible, those who are interested in the inpatient option will be admitted to the Clinical Neuroscience Research Unit (CNRU) of the Connecticut Mental Health Center (CMHC) for the 3 - 4 week stay that will involve medication initiation and laboratory sessions where subjects will be exposed to stress, drug cues and neutral-relaxing cues on three separate consecutive days. Lab sessions will take place either on the Clinical Neuroscience Research Unit (CNRU) or at the Yale Stress Center.

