with medication and alcohol withdrawal/anxiety, we used a conservative effect size of $d = .60$ for detection of significant main effects and possible interactions in the clinical trial. At this effect size and power = .80, with $p < .05$, sample size estimates from Cohen (1988, p.258) indicated that we would require 25 subjects per cell to adequately assess the proposed hypotheses for the clinical trial (total $N = 100$). Including a 15-20% drop-out after enrollment, we estimated recruitment of 120 AD patients into the trial to ensure adequate power for the trial.

Data Analysis for Laboratory Study: Repeated measures ANOVA and mixed model procedures to assess treatment group differences in alcohol craving and stress related changes (heart rate, blood pressure, HPA and catecholamine responses) during laboratory exposure to stress and drug cues as compared to neutral imagery conditions. Non-parametric tests will be used to assess occurrence of side effects, treatment retention rates, alcohol use measures, CIWA scores and perceived stress scores during the outpatient treatment phase. The number and type of AE's for the two treatment groups will be conducted using t-tests, chi-square tests and ANOVAs as appropriate. Findings will be used to estimate effect sizes for the medication and guide the larger randomized clinical trial.

Data Analysis for the 12-week clinical trial Study: For this phase, the following moderator and primary and secondary outcomes are specified:

Primary Moderator Measure: Alcohol withdrawal symptoms, as measured by the CIWA alcohol withdrawal scale,

Primary Outcome Measures in the outpatient treatment phase: These are: (1) Heavy drinking days (5 or more for men, 4 or more for women) during the 12 week period, and (2) Any drinking days. Both will be assessed daily using smartphone or interactive voice recording surveys completed by the patients and also with weekly urine drug screens/breathalyzer reports and self report of drug use on the Substance Use Calendar.

Secondary Outcome Measures in the outpatient treatment phase: Secondary outcome measures will include alcohol craving scales, anxiety (Hamilton Anxiety Scale) and depression (CES-D) and sleep quality using the Pittsburgh Sleep Quality Index – PSQI).

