Data Analytic Procedures: Since patients will be randomly assigned to the Prazosin and PLA treatment groups and Intent-to-Treat (ITT) analyses will be conducted for the clinical outcomes. We do not expect the groups to be different on demographic, prior drug use history or other predictor variables. Nevertheless, prior to undertaking the specific analysis for each aim, we will compare the treatment groups on demographic variables, substance use characteristics and previous psychiatric history/predictor variables using t-tests/chi-square analyses as appropriate. If any group differences are found, the specific variable will be entered as a covariate in all of the specific analyses. As there are no established thresholds for AW effects on drinking outcomes in outpatient treatment, baseline AW will be assessed as continuous measure in all overall analyses. Thus, intent-to-treat (ITT) analyses with baseline AW severity (mean-centered continuous CIWA-Ar scores) as a moderator of Time (Pre-Full Dose(FD): weeks 1-2; Post FD: weeks 3-12) were conducted with linear or generalized linear mixed effect (LME/GLME) piecewise growth models for continuous and binary outcomes. Due to a positive skew, number of drinks per day

(AvgD) will be log-transformed. Control variables in all analyses will be gender (0=male), inpatient (0=outpatient), and dropout (0=completer, 1=dropout/withdrawn prior to 4 weeks, 2=dropout/withdrawn after 4 weeks). For secondary outcomes linear mixed models with random intercepts will be used to assess the effect of AW, Treatment and Week (factor 1-12, or Weeks 4, 8 and 12) on the secondary outcome variables. All control variables from the main outcome analyses are included in the secondary outcome analyses. If significant interactions with AW are observed for primary or secondary outcome analyses, a median split of AW scores will be conducted to obtain Low and High AW groups and assess contrasts by treatment.

Aims and Hypotheses for Laboratory and Treatment Outcome Components: All analyses of the laboratory and the treatment components will be based on the following specific aims and hypotheses:

Specific Aim 1: To evaluate the effects of Prazosin on stress-induced alcohol craving and associated neuroadaptations in alcohol dependent individuals. Hypothesis 1: Prazosin will decrease stress-induced alcohol craving and negative emotions in the laboratory as compared to placebo.

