This aim will be tested using mixed model analysis of variance procedures for each of the following dependent measures: VAS alcohol craving scale; VAS anxiety scale; brief CCQ; DES emotions of anger, sadness and fear; heart rate, blood pressure and HPA measures of ACTH and cortisol and NE and EPI.

Specific Aim 2: To evaluate the efficacy of Prazosin versus Placebo in high alcohol withdrawal individuals on primary outcomes of: (a) heavy drinking days (HDD) over 12 week period; (b) Any drinking days (DD%).

Hypothesis 2: In high alcohol withdrawal individuals, Prazosin group will show significant reductions in HDD% and DD% during the 12 week treatment period as compared to Placebo group. No differences between medication treatment groups in the Low alcohol withdrawal individuals will be observed.

Secondary outcome measures such as alcohol craving, Anxiety, depression and sleep quality will be assessed. Findings PSS, COPE and LES scores will be examined.

SECTION VI: RESEARCH INVOLVING DRUGS, BIOLOGICS, RADIOTRACERS, PLACEBOS AND DEVICES
--

If this section (or one of its parts, A or B) is not applicable, state N/A and delete the rest of the section.

A. DRUGS, BIOLOGICS and RADIOTRACERS

1. **Identification of Drug, Biologic or Radiotracer:** What is (are) the **name(s)** of the drug(s) biologic(s) or radiotracer(s) being used? Identify whether FDA approval has been granted and for what indication(s).

Prazosin (marketed by Pfizer Inc) is an alpha-1-adrenergic agonist that is known to preferentially bind to post-synaptic alpha1-adrenergic receptors. Walker et al (2008) found that Prozaosin was effective in suppressing excessive alcohol consumption in rats, suggesting the involvement of the noradrenergic system in alcohol dependence. Simpson et al. (2007) found similar findings in a pilot trial using prozosin for treatment of alcohol dependent men and women. Prazosin therefore is an excellent candidate for treating alcohol seeking behaviors. It may also be more easily tolerated than those medications which directly modulate these transmissions.

All protocols which utilize a drug, biologic or radiotracer **not** approved by, but regulated by, the FDA, or a radiotracer regulated by the RDRC, must provide the following information:

- What is the Investigational New Drug (IND) **number** assigned by the FDA? N/A
- Who holds the IND?
- All protocols which utilize a radiotracer not approved by, but regulated by the FDA must provide the IND number: _____

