Simpson et al (2007) report that when administering 16mg per day of the drug, blood pressure changes were more evident in the prazosin group; however, the drop was still within the normal range. Raskind et al. 2002, prescribed up to 20mg a day of the study medication. Three of the 36 subjects reported orthostatic dizziness, headache, and lethargy, however no subject experienced syncope or a fall. The researchers report that previous administration of Prazosin for hypertension and benign prostate hypertrophy has shown that adverse effects tend to occur at initial lower doses rather than at higher doses. Raskind et al, 2007 used a maximum dosage of 15mg which was maintained for 8 weeks. No significant differences in supine or standing blood pressure were found between the placebo and Prazosin groups. Transient dizziness was reported by some subjects, however, most of these subjects were also receiving concurrent antihypertensive or psychotropic medication, and was also reported by subjects in the placebo group. Therefore, it appears that a maximum maintenance dosage of 16mg of prazosin will be generally tolerable and safe for use in the proposed adult sample of subjects.

3. **Source:** a) Identify the source of the drug or biologic to be used.

Commercially available Prazosin capsules will be used. Prazosin HCl (generic) is marketed by Mylan Pharmaceuticals Inc in capsules containing 1mg, 2mg, or 5mg of prazosin as the hydrochloride. The placebo medication will be prepared by the CMHC pharmacist. Both the Prazosin and the placebo will be dispensed by the CMHC pharmacist / YNHH IDS.

Prazosin pills will be purchased through the CMHC pharmacy / YNHH IDS, and the research pharmacist will make up identical active and placebo capsules for medication administration. Subjects will be randomly assigned to three times daily dosing of Prazosin/placebo (with the exception of day 1 which is once daily, and days 2-3 twice daily).

During weeks 1-4, inpatient subjects will self-administer study medication three times daily under supervision by nursing staff on the CNRU who will also monitor vital signs three times daily and side effects. Urines, alcohol craving, abstinence symptoms, mood and perceived stress scale and side effects will be assessed three times weekly.

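### If ward days count as non-drinking, the time-constant inpatient covariate lets chance plan imbalance between arms into the treatment-by-time terms of the 12-week primary models

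*Combined protocol and SAP*

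**What the plan says.** Section V, item 12 lists the drinking outcomes under the heading "Primary Outcome Measures in the outpatient treatment phase". The first is nevertheless "1) Heavy drinking days (5 or more for men, 4 or more for women) during the 12 week period", and Hypothesis 2 predicts that the "Prazosin group will show significant reductions in HDD% and DD% during the 12 week treatment period". Data Analytic Procedures fits linear or generalised linear mixed piecewise growth models with "Time (Pre-Full Dose(FD): weeks 1-2; Post FD: weeks 3-12".

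The Research Plan lets patients choose their setting. The inpatient-outpatient plan "involves 3 - 4 weeks of inpatient treatment followed by 8 - 9 weeks of outpatient treatment", and Section VI, A.3 states: "During weeks 1-4, inpatient subjects will self-administer study medication three times daily under supervision by nursing staff on the CNRU".

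The only adjustment for setting is a fixed indicator: "Control variables in all analyses will be gender (0=male), inpatient (0=outpatient", alongside a dropout category. A baseline variable that differs between arms would also enter only as a covariate. Random effects are named for the secondary analyses ("For secondary outcomes linear mixed models with random intercepts will be used") but not for the primary models. Section VI, A.3 says that the pharmacy randomises; no stratification by plan is described.

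On measurement, the Substance Use Calendar is completed weekly during treatment and ward urines check sobriety, so ward days can be recorded. The daily phone or app reports are described for outpatients, and Section X, item 2 pays for them on the inpatient-outpatient plan only during the outpatient phase.

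**The concern.** For inpatient-plan patients the 12-week window mixes two settings, and the change of setting falls early in the second time segment. If ward weeks are recorded as near-zero drinking, these patients show a rise at discharge that has nothing to do with the drug. A 0/1 covariate moves all 12 weeks by the same amount and cannot describe that shape. If the arms happen to differ in their share of inpatient-plan patients, the leftover shape is credited to treatment-by-time. The same happens to treatment-by-withdrawal-by-time if the gap exists only among high-withdrawal patients. At stake is the credibility of the time-related treatment terms in the primary models, not the 12-week mean difference.

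**Working it through.** **What the documents give.** Stay 21-28 of 84 days (21/84 = 25%, 28/84 = 33%); knot between weeks 2 and 3; 75 per arm (dosing table). They give no inpatient share, drinking rate or SD, and no figure of their own on this point to reproduce.

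**Assumptions.** Ward weeks = 0; otherwise 3 drinking days per week (range 2-4); half inpatient; no drug effect; joined line segments over weeks 1-2 and 2-12; exchangeable within-patient correlation.

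**False slope for a given plan gap.** Week 1 has its own fitted value, so the post-full-dose slope is that of a straight line through weeks 2-12. Write x = week - 2 (0 to 10, mean 5, sum of squares about the mean 110). The inpatient-minus-outpatient difference is -3 in ward weeks and 0 afterwards.
- 3-week stay (x = 0, 1): [(-5)(-3) + (-4)(-3)]/110 = 27/110 = 0.245.
- 4-week stay (x = 0, 1, 2): (15 + 12 + 9)/110 = 36/110 = 0.327.

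False treatment-by-post slope = plan gap × this difference:

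| Plan gap | 3-week stay | 4-week stay |
|---|---|---|
| 10 points (45/55) | 0.0245 | 0.0327 |
| 20 points (40/60) | 0.0491 | 0.0655 |

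Units are drinking days/week per week; the arm with more inpatients appears to worsen. For a 10-point gap, 2 or 4 drinking days per week gives 0.016-0.044. With inpatient-by-segment terms every entry is 0. A 10-point gap confined to high-withdrawal patients gives the same 0.0245/0.0327 in the treatment-by-withdrawal-by-post term.

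**The 12-week mean.** The covariate removes the plan mean (-3 × 3/12 = -0.75 for 3 weeks). At a 10-point gap the residual treatment difference is 0.10 × (-3 + 0.75) = -0.225 in week 1 and -0.102 in week 2. Weeks 3-12 sum to 10 × (-0.1023) + 0.02455 × 55 = +0.327. The total is -0.225 - 0.102 + 0.327 = 0.

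**Other codings.** With a simple pre/post step and 25-50% drinking days, a 10-point gap moves the term by 2.0-4.5 percentage points: 0.10 × 25 × 0.8 to 0.10 × 50 × 0.9. For a binary outcome at 3/7 drinking days, the false odds ratio over the 10 post weeks is 1.17 (3-week stay) or 1.26 (4-week stay).

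**How often such gaps arise.** Two independent binomials, half inpatient: a gap of 10 points or more has probability 22% at 75 per arm and 42% at 37 per arm (roughly half of each arm, as in a median split). If a quarter are inpatient, these are 16% and 35%. A gap of 20 points or more: 2% and 8%.

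**Simulated test size.** 150 patients, unstratified, no effect, 2,000 runs, nominal 5%, weekly SD 1.5 / 2.0 / 2.5:

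| Random intercepts only | 3-week stay | 4-week stay |
|---|---|---|
| Constant covariate | 12.9 / 11.1 / 10.7% | 20.1 / 17.3 / 16.2% |
| With inpatient-by-segment terms | 3.4 / 4.9 / 5.6% | 5.7 / 7.2 / 8.3% |

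Repeat runs widen the first row to about 10-14% and 16-22%, and leave about 7-10% for a 4-week stay with the terms, because line segments with a week-2 knot do not fit a step at discharge.

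With random slopes and the constant covariate, rejection is 1.0-3.6%. The mean standard error (SD 2.0) is 0.0391/0.0404 against 0.0278/0.0283 with the terms, ratios of 1.41 and 1.43.

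Cluster-robust errors, in a separate simulation of 100 patients, give 6-7% over random allocation. At a fixed 20-point gap they still reject 19% for the post slope, against 6% once the terms are added.

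**Dilution, which is separate.** With equal plan shares and an assumed effect of -0.90 from week 1, the fitted week-2 difference shrinks to -0.90 + 0.5 × 0.90 × (1.773/3) = -0.63 for a 3-week stay, and to -0.53 for a 4-week stay. The added terms do not undo this.

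**The case against.** The strongest objection is that ward zeros are assumed. The primary outcomes are to be assessed by daily phone or app reports, which the documents describe for outpatients. If the heading governs, ward days are missing or out of scope and the mechanism does not operate. That stands: the documents establish a conflict to be reconciled, and the arithmetic applies only on one reading.

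Second, plan imbalance is a chance event under randomisation, so there is no average bias. Hypothesis 2 is worded as reductions over the 12 weeks, and no section names the treatment-by-post slope as the deciding test. This also stands and limits the point to error given the actual allocation and to the standard errors of the time terms.

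A reader might infer that the primary treatment effect is biased, or that the trial's test will reject too often. The documents support neither. The 12-week mean difference is unaffected by plan imbalance, and over-rejection occurs under random intercepts only, a structure stated for the secondary outcomes alone. With random slopes the cost is lost precision.

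Third, the added terms are not a complete cure. They leave some excess for a 4-week stay under random intercepts, and in a binary model all-zero ward weeks cause separation, with no finite estimate for the inpatient terms. Both limits are accepted in the fix. What the objection does not remove is that a constant covariate has the wrong shape if ward days are counted.

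**Conclusion.** The concern holds in a conditional form, as a cheap improvement. The mismatch between heading and window, the 3-4 ward weeks and the time-constant covariate are in the text. The consequence requires that ward days be scored as non-drinking. Plan imbalance then distorts the treatment-by-time terms for the allocation obtained, by the amounts tabulated above for an assumed 3 drinking days per week. How this reaches the test depends on the unstated random effects: too many rejections with random intercepts only, or a standard error about 40% too large with random slopes. Inpatient share, drinking rate, SD and exact ward zeros are all assumptions, so the sizes are indicative. The direction of the argument and the exact zero for the 12-week mean do not depend on the drinking rate.

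**What to change.** 1. Reconcile the outcome heading with the 12-week window, and state whether ward days belong to the outcome and from which source they are scored.
2. If they belong, add inpatient-by-pre-full-dose and inpatient-by-post-full-dose terms to the linear primary models. Define inpatient as the plan chosen at entry, because the Outpatient Plan allows inpatient treatment to be offered later.
3. State the random effects of the primary models. Use random slopes or cluster-robust standard errors with the two terms: the terms alone leave some excess rejection for a 4-week stay, and robust errors alone do not correct the estimate for the imbalance obtained.
4. For binary outcomes, use a penalised fit or analyse only non-hospital days, to avoid separation.
5. Report the percentages of heavy drinking days and of any drinking days on non-hospital days as a sensitivity analysis.

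The cost is two model parameters and one extra analysis, with admission and discharge dates in the analysis data. Design and enrolment do not change. The diluted early contrast remains and should be acknowledged when the pre-full-dose segment is interpreted.

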The Structured Clinical Interview for DSM-IVTR (SCID, First et al., 1995) will be used to obtain DSM-IVTR Alcohol Dependence and other substance use disorder diagnoses. The SCID's reliability and validity among substance-using populations has been established in large-scale surveys (Kranzler et al., 1996). The number of dependence syndrome elements endorsed from the DSM-IVTR substance abuse/dependence criteria will assess severity of alcohol and other drug dependence. The SCID will also be used to obtain previous psychiatric diagnoses.

Medical History and Physical Examination: All patients will be required to participate in a physical examination including a medical history, electrocardiogram (EKG), blood and urine laboratory assessments prior to initiation of Prazosin to ensure eligibility for Prazosin study protocol. These will be conducted at the CNRU.

Short Form 36 Health Survey (SF-36) is a 36-Item questionnaire used in to assess the subjective quality of life of respondents.

Drug and Alcohol Use Measures:

Addiction Severity Index (ASI: McLellan et al., 1992) is a structured interview that assesses the severity of substance use and substance-related problems in the areas of medical, employment, legal, family/social and psychiatric functioning. The ASI is the most widely used instrument for assessment of substance use and related problems and its psychometric properties are well-established (Cacciola et al., 1997). The ASI will be used at pre-treatment and week 9. Follow-up ASI interviews will be conducted at 30 days post-treatment.

The Substance Use Calendar was developed by Miller and DelBoca (1994) and is based on the Time-Line Follow-Back Method (TLFB) (Sobell, Maisto et al. 1980). The SUC uses a calendar prompt and a number of other memory aids (e.g., holiday, payday, and other personally relevant dates) to facilitate accurate recall of daily drug use during the targeted period. It has demonstrated adequate levels of reliability and validity when administered as an in-person interview, over the telephone, and when administered via computer (e.g. Carey, 1997; Sobell, Brown, Leo, & Sobell, 1996; Sobell, Sobell, Leo & Cancilla, 1988). It's reliability and validity in drug abusing samples has also been established (Fals-Stewart, et al., 2000). In the current study we will use to obtain self-report of day to day use of alcohol and drugs, for the 60 days prior to treatment, weekly during treatment, and at the 30 day follow-up interviews.

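### Beyond the fixed control variables, covariates are chosen by baseline significance tests, so pre-treatment drinking is adjusted for only if it happens to be imbalanced

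*Combined protocol and SAP*

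**What the plan says.** The relevant text is in Section V, item 12, under Data Analytic Procedures. After noting random assignment, the plan says "We do not expect the groups to be different on demographic, prior drug use history or other predictor variables". It nevertheless plans a screening step: "we will compare the treatment groups on demographic variables, substance use characteristics and previous psychiatric history/predictor variables using t-tests/chi-square analyses as appropriate". The result is binding: "If any group differences are found, the specific variable will be entered as a covariate in all of the specific analyses". No significance level is given for the screen, and the variables to be screened are described by type, not listed.

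The same section fixes several terms independently of the screen. For withdrawal severity, "baseline AW will be assessed as continuous measure in all overall analyses", entered as a mean-centred CIWA-Ar score that moderates the time terms. Further, "Control variables in all analyses will be gender (0=male), inpatient (0=outpatient), and dropout". For the secondary outcomes, "All control variables from the main outcome analyses are included in the secondary outcome analyses".

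Pre-treatment drinking is not among the fixed terms. It is collected: under Drug and Alcohol Use Measures (Section V, item 3), the Substance Use Calendar records day-by-day alcohol use "for the 60 days prior to treatment, weekly during treatment, and at the 30 day follow-up interviews".

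**The concern.** Under randomisation, any baseline difference between arms is a chance event. A test of that difference carries no information on whether the variable predicts drinking, yet prediction is what makes a covariate worth including. The rule therefore tends to leave out prognostic variables, because most of them will balance, and it lets in unrelated ones that happen not to.

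Pre-treatment drinking is the obvious example. The outcomes are heavy drinking days and any drinking days, and recent drinking is a natural candidate predictor of both. The piecewise time structure does not supply it, because its first segment is weeks 1-2, when patients are already on study medication.

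Two things are at stake. One is the precision of the treatment comparison. The other is whether the covariate set can be written down before the data are seen; with no threshold and no list of variables, it cannot.

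**Working it through.** **The plan's own figure.** Power Analysis (Section V, item 12) says "we used a conservative effect size of $d = .60$ for detection of significant main effects and possible interactions in the clinical trial" and arrives at 25 per cell, N = 100, for power .80 at p < .05. A two-sided comparison of two means at d = 0.60 needs 44 per arm (normal approximation) or 45 per arm (t), so N = 88 to 90. The main effect in a 2x2 analysis of variance with f = 0.30 also needs N = 90. The stated 100 is not reproduced exactly, but it is larger than needed for a main effect and gives power of about 0.84 (t). Nothing below depends on this gap; 50 per arm is taken from N = 100.

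**How often a variable is left out.** With screening level a, a variable is omitted with probability 1 - a. The plan states no level, so a is an assumption: .05 gives 95% omitted and .10 gives 90%.

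**Analytic check of the gain from adjustment.** Let the outcome SD be 1 and let rho be the correlation of the covariate with the outcome (assumed; not in the documents). Adjustment reduces the residual SD to sqrt(1 - rho²). Power is approximately Phi(d / (SD x sqrt(2/n)) - 1.96). With n = 50 and d = 0.60:

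- Unadjusted: 0.60/0.20 = 3.00; Phi(1.04) = 0.85.
- rho = 0.5: SD = sqrt(0.75) = 0.866; 0.60/(0.866 x 0.20) = 3.46; Phi(1.50) = 0.93.

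**Simulation of the rule itself.** There were 40,000 runs per setting, with two arms, one continuous covariate, screening at .05 and two-sided tests at .05.

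| Per arm | rho | Power, never adjust | Power, plan's rule | Power, always adjust |
|---|---|---|---|---|
| 50 | 0.3 | 0.842 | 0.844 | 0.870 |
| 50 | 0.5 | 0.845 | 0.855 | 0.926 |
| 50 | 0.7 | 0.843 | 0.861 | 0.985 |
| 25 | 0.3 | 0.544 | 0.544 | 0.572 |
| 25 | 0.5 | 0.546 | 0.550 | 0.657 |
| 25 | 0.7 | 0.546 | 0.559 | 0.818 |

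At 50 per arm and rho = 0.5, the rule recovers 0.855 - 0.845 = 0.010 of an available 0.926 - 0.845 = 0.081, roughly an eighth. The 25-per-arm rows correspond to one withdrawal stratum of the plan's 2x2 layout, the setting closest to Hypothesis 2.

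**Type I error, 50 per arm.** For rho = 0.3, 0.5 and 0.7:

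- Under the rule, overall: 0.047, 0.043, 0.036.
- Always adjusting: 0.049, 0.048, 0.049.
- Among trials where the baseline p lies between .05 and .20, so the rule leaves the variable out: 0.059, 0.088, 0.114 unadjusted, against 0.049, 0.051, 0.049 adjusted.

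Overall the rule is slightly conservative. The conditional figures show that it fails to adjust where moderate chance imbalance makes adjustment most useful.

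**The case against.** The best defence is that the plan already has a prespecified core. Baseline CIWA-Ar, gender and inpatient status are in every main model, and the screen can only add to them. A reader might infer from the screening rule that chance imbalance determines the whole primary model, or that no covariates are fixed. The text does not support that: the rule governs only the additional terms.

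A reader might also infer inflated false-positive rates. The simulation shows the opposite overall (0.036 to 0.047).

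Nor is it alarming in itself that some covariate may enter by chance. With 10, 15 or 20 independent tests at .05, the probability is 1 - .95^k = 40%, 54% or 64%, but the level, the number of tests and their independence are all assumed. An unneeded covariate also costs little. One that just reaches p = .05 at N = 100 has R² with treatment of about 1.98²/(1.98² + 98) = 0.039, so the standard error rises by 1/sqrt(1 - 0.039), about 2%. The cost lies in what is left out, not in what gets in.

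It is also fair that power under the rule at 50 per arm (0.84 to 0.86) stays above the .80 target, that the gain depends on an unknown correlation, and that a single-covariate two-arm model is not the planned piecewise mixed model. Finally, a rule stated in advance limits analyst discretion to some extent, although here it has neither a threshold nor a list of variables.

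These points limit the size of the problem. They do not justify selecting covariates by imbalance, or leaving pre-treatment drinking to chance when it is already collected.

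**Conclusion.** The point holds in limited form. Outside the fixed terms, covariates are selected on chance imbalance rather than prognosis, and pre-treatment drinking is exposed to that selection. If screening is at .05, it is omitted about 95% of the time.

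The consequence is lost precision and a model that depends on the data. At 50 per arm and d = 0.60, power is 0.84 to 0.86 under the rule against 0.87 to 0.99 with routine adjustment, for assumed correlations of 0.3 to 0.7. These are simple two-arm figures, and the gain in the planned mixed models may be larger or smaller. The documents do not support a claim of inflated overall type I error, of a primary model without fixed covariates, or of a trial that misses its power target because of this rule. It is a worthwhile, nearly free improvement rather than a threat to validity.

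**What to change.** In Data Analytic Procedures:

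- Delete the rule that enters a variable because a baseline test finds a difference. A descriptive comparison of the arms can remain, provided that it does not determine the model.
- Name pre-treatment drinking, derived from the 60-day Substance Use Calendar, as a prespecified covariate for both primary outcomes. State the summary to be used, for example the percentage of heavy drinking days or of any drinking days to match the outcome.
- For each secondary outcome, prespecify its own baseline value where one is collected.
- Keep the existing baseline terms of gender, inpatient status and continuous baseline CIWA-Ar.

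The dropout category is also a fixed control, but it is defined after randomisation. Whether it should stay is a separate issue that this change does not settle.

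The cost is a few lines of SAP wording. The drinking data are already due to be collected, so no added visits, assessments or patients are needed.
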